**Introduction / Theoretical foundations:**

Transitory elastography is a non-invasive diagnostic method that has been used for the diagnosis and follow-up of patients with clinically significant portal hypertension (CSPH). In this context, the use of targeted therapies to reduce complications resulting from this finding plays a crucial role in managing these patients.

Carvedilol is a non-selective beta-blocker currently considered the first-line drug for treating patients with CSPH. Regarding its pharmacokinetic characteristics, its half-life is approximately 7 to 10 hours. However, there is still a debate in dosing regimen, specially regarding dose interval, with a potential lower bioavailability in once daily regimens

Nevertheless, although the dosing frequency may influence portal pressure and cardiac function, the direct impact on the value of splenic and liver elastography is not fully understood, and there are no studies directly comparing and evalutiang this topic. Therefore, focused studies assessing the impacto f once-daily vs twice daily dosing regimens become essential to improving clinical practice.

**Objectives:** To assess the acute effects of carvedilol posology in patients with clinically significant portal hypertension (CSPH), as a surrogate marker of bioavailability.

**Study design:** experimental study including patients with CSPH considered responders to carvedilol prescribed twice daily. These patients had their spleen stiffness measurement (SSM) and liver stiffness measurement (LSM) measured through elastography after suspending their second daily carvedilol intake. Results from the SSM were compared with the values measured while under treatment and before being prescribed with carvedilol. Additionally, comparisons for under treatment with carvedilol and 24-hour suspension were stratified according to carvedilol daily dosage, D'Amico classification, the Model for End-stage Liver Disease (MELD) scores, Child-Pugh score, and aetiologies for portal hypertension. The same procedure was repeated for the results of LSM.

**Target population:** patients with CSPH considered responders to carvedilol prescribed twice daily

#### **Inclusion and exclusion criteria:**

##### **Inclusion criteria**

- Patients with CSPH (defined as a LSM  $\geq$  25 kPa or SSM over 45kPa prior to introduction of carvedilol)

##### **Exclusion criteria**

- Non-responders to NSBB (defined as a reduction of their SSM of less than 10%)
- Patients under treatment with any NSBB other than carvedilol
- Patients with a dosing regimen other than twice daily
- Patients with contraindications to NSBB use
- Patients who had not been performed a SSM or LSM through TE while under treatment within 3 months prior to the beginning of the study
- Obesity (defined as body mass index (BMI)  $> 30 \text{ m/kg}^2$ )
- Patients with portal venous thrombosis
- Patients who refused to participate in the study

**Recruitment and Selection Process of Participants:** Patients admitted to the Liver Unit after meeting the inclusion and exclusion criteria, provided that they agree to participate after being adequately informed about the study.

**Variables:** gender, age, aetiologies for CSPH, D'Amico classification, the Model for End-stage Liver Disease (MELD) scores (both MELD-Na, and MELD 3.0), Child-Pugh score, and carvedilol daily dosage

**Potential benefits/risks of the study:** To assess if twice a day prescription may be better in keeping bioavailability of carvedilol and the intended effects of the treatment for CSPH throughout the day.

**Confidentiality and Anonymity:** Throughout the research development and presentation of results, confidentiality and anonymity of the participants are ensured. When transferring clinical data to the database, each participant will be assigned a code number that allows for

the decoding of their identity. The code will only be accessible to the researchers and will be stored separately from the main database. Access to the computer containing the aforementioned information will be restricted, requiring a specific username and password for each investigator.

**Dissemination of Results:** The intention is to publish the work in a national/international scientific journal

**Duration of the research study:** This is a study that will take place over a period of 1 month.

**Ethical considerations:** The present study will be approved by the ethics committees of each center and will follow the guidelines of Good Clinical Practice, the Declaration of Helsinki, and local laws, as well as the Regulation of the European Parliament and of the Council (EU) 2016/679 on the protection of individuals with regard to the processing of personal data, which was enacted on April 27, 2016.

**Direct and indirect costs for CHTMAD and other participating centers:** None

**Funding and insurance:** None

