Eligible patients were contacted by telephone up to 3 days prior to their appointment and assessed for enrolment. Patients were asked to suspend the night dose of carvedilol and postpone the morning dose until LSM and SSM were measured. After enrolment, patients could be excluded from the study if they failed to comply to the study regimen (last dose of carvedilol within 24 hours or related with TE protocol, namely overnight fasting), evaluated during their appointment. Informed consent were obtained from each patient included in the study.

Data Collection

For each patient, data on gender, age, aetiologies for CSPH, *D'Amico* classification, the Model for End-stage Liver Disease (MELD) scores (both MELD-Na, and MELD 3.0), Child-Pugh score, and carvedilol daily dosage were collected (22-25). For CSPH due to cirrhosis, the diagnosis of cirrhosis was based on previous biopsies or compatible clinical, biochemical, and imagiologic findings.

LSM and SSM were assessed by TE using FibroScan® 630 Expert (Echosens, Paris, France)

and values were obtained according to the recommendations of the European Federation of Societies for Ultrasound in Medicine and Biology (EFSUMB) (26). For each patient, LSM and SSM values were considered adequate if the interquartile range (IQR) was < 30% of the median value. The values were obtained, after overnight fasting, with the patient in a supine position with maximal abduction of the left arm; the probe was positioned in an intercostal space where the spleen was correctly visualized by US. LSM and SSM were expressed in kilopascal (kPa).

Data on the most recent TE in the previous 3 months and the TE performed before introduction of carvedilol were also collected through the electronic medical records of the enroled patients.

Blood chemistry tests were also performed during the appointment and results on haemoglobin, platelets, albumin, aspartate transaminase (AST), alanine transaminase (ALT), alkaline phosphatase, gamma-glutamyltransferase (GGT), total and direct bilirubin, sodium, creatinine and international normalize ratio (IQR) were collected.

Sample Size

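### The study measures the effect of one omitted night dose in patients taking carvedilol twice daily, so its conclusion should be limited to that and not extended to once- versus twice-daily dosing or to bioavailability

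*Protocol*

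**What the plan says.** **Stated purpose.** The protocol's introduction says that studies of "once-daily vs twice daily dosing regimens become essential to improving clinical practice". Under potential benefits and risks, the aim is "To assess if twice a day prescription may be better in keeping bioavailability of carvedilol and the intended effects of the treatment for CSPH", over the whole day. The objective is "To assess the acute effects of carvedilol posology in patients with clinically significant portal hypertension (CSPH), as a surrogate marker of bioavailability".

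**What is done.** The exclusion criteria remove "Patients with a dosing regimen other than twice daily". In the SAP (Participants), "Patients were asked to suspend the night dose of carvedilol and postpone the morning dose until LSM and SSM were measured". A patient can be excluded after enrolment for non-compliance, which includes "last dose of carvedilol within 24 hours". The SAP's Sample Size section sizes the study for suppression of one dose: SSM rising from 35.8 to 48.3 kPa, with a standard deviation (SD) of 19.2 kPa. The blood tests listed under Data Collection do not include a carvedilol level.

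**The on-treatment comparator.** This is the most recent transient elastography (TE) in the previous 3 months, taken from the records. Eligibility requires an earlier "SSM or LSM through TE while under treatment within 3 months prior to the beginning of the study". Daily carvedilol dosage is listed once, as a patient variable. The plan does not say that it is collected for the date of the comparator TE, and it does not require the same dose at both TEs.

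**The concern.** To say that twice-daily prescription is better requires something to compare it with, and the introduction supplies once-daily dosing. No once-daily regimen is observed. Omitting the night dose lengthens the interval to about 24 h, but it also removes part of that day's drug. It is therefore neither the full daily amount taken once nor a settled regimen of one unchanged dose per day. The documents do not say which of these once-daily prescription would mean. A rise in SSM would show how far the effect wears off about 24 h after the last dose. It would not show that one regimen is superior to the other. Without drug levels, stiffness alone cannot carry a conclusion on bioavailability either. The results are intended for publication, so the wording of the conclusion could influence prescribing.

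A second, smaller matter concerns the comparator. If a patient's dose or dosing frequency changed between the comparator TE and the appointment, the paired difference would mix that change with the omission.

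**Working it through.** **1. Purpose against procedure**

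| Element | Once- vs twice-daily question | One omitted dose |
|---|---|---|
| Introduction (protocol) | yes | |
| Benefit statement (protocol) | yes, by implication | |
| Objective (protocol) | open (posology, bioavailability) | open (acute effects) |
| Study design (protocol, SAP) | | yes |
| Procedure (SAP, Participants) | | yes |
| Sample Size (SAP) | | yes |

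The design, procedure and sizing agree with each other. The mismatch is with the stated purpose.

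**2. The plan's own figure**

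The difference is 48.3 − 35.8 = 12.5 kPa. A one-sided two-group formula gives 2 × (1.645 + 0.842)² × (19.2/12.5)² = 29.2, so 30 per group, and 30 × 1.1 = 33. A two-sided paired t-test also reaches 30 if 19.2 kPa is the SD of single measurements and the within-patient correlation is about 0.25. The SAP does not say which was used, and this point does not depend on it. Evaluable patients: 33 × 0.9 = 29.7, about 30.

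**3. How the omitted-dose level relates to once-daily dosing**

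Input from the protocol: "its half-life is approximately 7 to 10 hours". Assumptions: linear one-compartment kinetics, steady state, 12-h spacing, equal split doses. Let q be the fraction left after 12 h, q = 2^(−12/half-life). With a daily amount of 1:

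- Usual twice-daily 12-h trough: 0.5q/(1 − q)
- 24 h after the last morning dose, night dose omitted: 0.5q²/(1 − q)
- Once-daily trough, same total dose: q²/(1 − q²)
- Once-daily trough, single dose unchanged: 0.5q²/(1 − q²)

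| | Half-life 7 h | Half-life 10 h |
|---|---|---|
| q | 0.305 | 0.435 |
| Omitted ÷ once-daily, same total = (1 + q)/2 | 0.65 | 0.72 |
| Omitted ÷ once-daily, single dose unchanged = 1 + q | 1.30 | 1.44 |

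The split between morning and night doses is not given. If the morning dose is a share f of the daily amount, the two ratios become f + (1 − f)q and [f + (1 − f)q]/f. For f from one third to two thirds they range over 0.54-0.81 and 1.15-1.87. The omitted-dose level always lies between the two once-daily troughs.

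**4. The fall in level**

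This is the fall from the on-treatment level after omission, divided by the fall under true once-daily dosing, with equal split doses. It depends on when the comparator TE was taken after a dose, which the plan does not fix.

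| Comparator TE | Same total dose | Single dose unchanged |
|---|---|---|
| 12 h after dosing (trough) | 1.30-1.44 | 0.81-0.91 |
| 4 h after dosing | 1.09-1.15 | 0.91-0.96 |

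A ratio above 1 means that omission overstates the fall, and below 1 that it understates it. Both occur. All of these figures describe drug level, not stiffness.

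**5. Precision of a same-regimen sensitivity analysis**

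Two-sided paired t-test at .05, difference 12.5 kPa. The 95% confidence interval (CI) half-width is t × SD/√n. The first SD reading takes 19.2 kPa as the SD of differences. The second takes it as the SD of single measurements with correlation 0.3, so the SD of differences is 19.2 × √(2 × 0.7) = 22.7 kPa. The two readings, the correlation and the subset sizes below 30 are assumptions.

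| n | SD 19.2: half-width, power | SD 22.7: half-width, power |
|---|---|---|
| 30 (all) | 7.2 kPa, 0.93 | 8.5 kPa, 0.83 |
| 27 | 7.6 kPa, 0.90 | 9.0 kPa, 0.79 |
| 20 | 9.0 kPa, 0.79 | 10.6 kPa, 0.65 |
| 10 | 13.7 kPa, 0.45 | 16.3 kPa, 0.34 |

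**The case against.** The mismatch is with a hedged line about potential benefit, which says only that twice-daily prescription may be better. The objective speaks of acute effects, and everything operational describes one omitted dose. No section plans a superiority claim. This stands, and it is why a change of wording is enough and no redesign is called for.

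The measurement also bears on the question. Stiffness 24 h after the last dose reflects whether the effect lasts to the end of a once-daily interval, and the drug level is bracketed by the two natural once-daily definitions. With a comparator TE 4 h after dosing, the fall ratios are close to 1. This stands too: the procedure is a relevant but indirect proxy.

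A reader might infer that omission overstates the loss from once-daily dosing. That holds only if once-daily means the same total dose, which the documents do not specify. With the single dose unchanged, the direction reverses.

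A reader might also infer that the paired comparison is biased by dose changes. The documents do not show that any dose changed, and the size of such a bias cannot be computed from them. It is a possibility to check, and only one of several ways in which the comparator TE may differ from the appointment TE.

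**Conclusion.** The point holds as a limit on what the study may conclude. It supports a statement on the change in SSM and LSM about 24 h after the last dose when one dose of a twice-daily regimen is omitted. It does not support a conclusion that twice-daily is superior to once-daily, or a conclusion on bioavailability. Its size can be given only as drug level: 65-72% of one once-daily trough and 1.30-1.44 times the other, under linear kinetics and equal split doses. The direction of the mismatch is undetermined, and no error in kPa follows. The documents do not support reading this as a flaw in the design or sizing, which are internally consistent. The dose check is secondary and minor. Overall this is a cheap improvement, held with medium confidence.

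**What to change.** 1. Reword the objective and the benefit statement, and limit the conclusion, to the change in SSM and LSM about 24 h after the last dose when one dose of an existing twice-daily carvedilol regimen is omitted. State that the study does not conclude that twice-daily is superior to once-daily and draws no conclusion on bioavailability. The background sentence in the introduction can stay.

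2. Secondary: take from the records the daily dose and dosing frequency at the comparator TE. Keep all patients in the main paired comparison, and add a prespecified sensitivity analysis limited to those on the same twice-daily dose at both TEs. Report that it addresses regimen change only. It does not deal with time since last dose at the comparator TE, the gap of up to 3 months, or selection of responders, so agreement with the main result should not be read as general reassurance.

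Cost: a narrower claim, one or two items from electronic records already in use, and one extra analysis with lower precision. The main comparison keeps its patients and its power, and no dose or procedure changes.

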Centro Hospitalar Trás-os-Montes e Alto Douro

STATISTICAL ANALYSIS PLAN

The impact of carvedilol posology on Clinically Significant Portal Hypertension: Insights from Elastography Measurements

31 May 2023

Participants and methods

Study Design

The present study was an experimental study conducted at the Liver Unit at Centro Hospitalar de Trás-os-Montes e Alto Douro, Vila Real, Portugal. Patients with CSPH considered responders to carvedilol prescribed twice daily were included. These patients had their SSM and LSM measured through TE after suspending their second daily carvedilol intake. Results from the SSM were compared with the values measured while under treatment and before being prescribed with carvedilol. Additionally, comparisons for under treatment with carvedilol and 24-hour suspension were stratified according to carvedilol daily dosage, *D'Amico* classification, the Model for End-stage Liver Disease (MELD) scores, Child-Pugh score, and aetiologies for PH. The same procedure was repeated for the results of LSM. This study was approved by the clinical research ethics committee of Centro Hospitalar de Trás-os-Montes e Alto Douro, in accordance with the 1975 Declaration of Helsinki declaration.

Participants

All patients over 18 years of age, followed at the Liver Unit at Centro Hospitalar de Trás-os-Montes e Alto Douro, Vila Real, Portugal for CSPH (defined as a LSM \geq 25 kPa or SSM over 45kPa prior to introduction of carvedilol) were eligible. Patients were excluded from the study if they were non-responders to NSBB (defined as a reduction of their SSM of less than 10%), were under treatment with any NSBB other than carvedilol, had a dosing regimen other than twice daily, had not been performed a SSM or LSM through TE while under treatment within 3 months prior to the beginning of the study, were obese (body mass index (BMI) $>$ 30 m/kg²), had contraindications to NSBB use, presented portal venous thrombosis or refused to participate in the study.

Eligible patients were contacted by telephone up to 3 days prior to their appointment and assessed for enrolment. Patients were asked to suspend the night dose of carvedilol and postpone the morning dose until LSM and SSM were measured. After enrolment, patients could be excluded from the study if they failed to comply to the study regimen (last dose of carvedilol within 24 hours or related with TE protocol, namely overnight fasting), evaluated during their appointment. Informed consent were obtained from each patient included in the study.

Data Collection

For each patient, data on gender, age, aetiologies for CSPH, *D'Amico* classification, the Model for End-stage Liver Disease (MELD) scores (both MELD-Na, and MELD 3.0), Child-Pugh score, and carvedilol daily dosage were collected (22-25). For CSPH due to cirrhosis, the diagnosis of cirrhosis was based on previous biopsies or compatible clinical, biochemical, and imagiologic findings.

LSM and SSM were assessed by TE using FibroScan® 630 Expert (Echosens, Paris, France)

and values were obtained according to the recommendations of the European Federation of Societies for Ultrasound in Medicine and Biology (EFSUMB) (26). For each patient, LSM and SSM values were considered adequate if the interquartile range (IQR) was < 30% of the median value. The values were obtained, after overnight fasting, with the patient in a supine position with maximal abduction of the left arm; the probe was positioned in an intercostal space where the spleen was correctly visualized by US. LSM and SSM were expressed in kilopascal (kPa).

Data on the most recent TE in the previous 3 months and the TE performed before introduction of carvedilol were also collected through the electronic medical records of the enroled patients.

Blood chemistry tests were also performed during the appointment and results on haemoglobin, platelets, albumin, aspartate transaminase (AST), alanine transaminase (ALT), alkaline phosphatase, gamma-glutamyltransferase (GGT), total and direct bilirubin, sodium, creatinine and international normalize ratio (IQR) were collected.

Sample Size

The sample-size calculation was based on the assumption of a SSM of 35.8 kPa during treatment and a detectable increase of 35.0% (48.3 kPa) while supressing one dose of carvedilol (1). We considered standard deviation as 19.2 kPa, an alpha of .05 and a power of .80. We also assumed that 10% of enroled patients might fulfil further exclusion criteria, by not following the study proposed regimen, totalling 33 patients needed to enrol in the study.

Data Analysis

Categorical variables were described with absolute and relative (%) frequencies and continuous variables were described with means and standard deviations (SD) when approximately normally distributed or with median an interquartile range (IQR) otherwise. Results from the SSM evaluation through TE at appointment were compared with the values measured before introduction of carvedilol and in the previous TE evaluation within 3 months, using paired t-tests. Further comparisons between SSM at appointment and within the previous 3 months were made stratifying for aetiology of portal hypertension, *D'Amico* classification, the Model MELD scores, Child-Pugh score, and carvedilol daily dosage. For the described analysis, aetiology was divided in alcoholic cirrhosis and non-alcoholic cirrhosis; in quartiles for MELD and Child-Pugh; and in above and below the median for carvedilol daily usage. The same procedure was repeated for LSM.

Data analysis was performed using R version 4.3.0 (R Foundation for Statistical Computing, Vienna, Austria). 95% confidence intervals (CI) for point estimates were calculated. P-values <.05 were considered statistically significant.

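### The on-treatment elastography used as comparator need not be on the same daily dose and twice-daily regimen as at the appointment, so a dose or interval change cannot be separated from the omitted dose

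*SAP*

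**What the plan says.** The appointment reading is controlled. Under the SAP (Participants), patients skip the night dose, delay the morning dose until after the measurement, and can be excluded if they do not comply.

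The other half of the pair comes from routine records. SAP, Data Collection: "Data on the most recent TE in the previous 3 months and the TE performed before introduction of carvedilol were also collected". SAP, Data Analysis, compares the appointment SSM with each of these two earlier values by paired t-tests, then repeats the procedure for liver stiffness (LSM).

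Three provisions bear on the earlier on-treatment reading:

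- **Timing and treatment status.** Patients are excluded if they "had not been performed a SSM or LSM through TE while under treatment within 3 months prior to the beginning of the study". The protocol's Exclusion criteria carry the same condition.
- **Regimen.** The protocol excludes "Patients with a dosing regimen other than twice daily", and the SAP excludes anyone who "had a dosing regimen other than twice daily". Both describe the patient, not the earlier TE.
- **Quality.** "For each patient, LSM and SSM values were considered adequate if the interquartile range (IQR) was < 30% of the median value". No TE occasion is named, and nothing is said about what happens to an inadequate value.

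Carvedilol daily dosage is listed among the data collected, with no statement that it is recorded as of each TE.

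**The concern.** The design reads the change from the earlier TE to the appointment as the effect of leaving out a dose. That requires the two readings to differ in the omission and, as far as possible, in nothing else about carvedilol. As written, a patient whose total daily dose was altered after the earlier TE is eligible. So is a patient who was on once-daily dosing at the earlier TE and later moved to twice daily. The second case touches the study question directly, because the protocol's introduction is about once-daily versus twice-daily dosing: that pair would not compare maintained twice-daily treatment with an omitted dose.

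A paired t-test removes stable differences between patients. It does not remove a within-patient change that falls between the two readings. If the dose at the earlier TE is not extracted, neither the analyst nor a reader can tell which pairs are affected.

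**Working it through.** **Step 1. What ties the two readings together.**

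- Recency: yes, the most recent TE within 3 months.
- On carvedilol at the earlier TE: yes, by the eligibility condition together with the exclusion of other NSBBs.
- Twice-daily regimen at the earlier TE: not stated. It can be inferred at most from the description of the population.
- Same total daily dose at both readings: not stated in either document.
- Dose at the earlier TE recorded: not stated in either document.

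**Step 2. What the paired test estimates.** For each patient, difference = (effect of omission) + (effect of any change in dose or regimen since the earlier TE) + noise. If a share q of patients changed and the change moved their difference by s kPa on average, then

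mean difference = mean omission effect + q × s.

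The t-test tests this sum. Its sign depends on the direction of change. On the assumption that more carvedilol lowers SSM, a lower dose at the earlier TE than now understates the omission effect, and a higher one overstates it.

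**Step 3. The plan's own figures (SAP, Sample Size).** On-treatment SSM is 35.8 kPa with a 35.0% increase: 35.8 × 1.35 = 48.3, a difference of 48.3 − 35.8 = 12.5 kPa. The enrolment figure of 33 can be recovered as 30 × 1.1. Here 30 comes from a one-sided two-sample formula, 2 × (19.2 × (1.645 + 0.842) / 12.5)² = 29.2, rounded up. That formula is not at issue here. It serves only to show that about 30 evaluable pairs are expected.

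**Step 4. Size of the bias, on assumed inputs.** The documents give neither q nor s. Take q = 10-30% and s = 10-20% of 35.8 kPa, all in one direction:

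- Low: 0.1 × 0.1 × 35.8 = 0.36 kPa; 0.36 / 12.5 = 2.9%.
- High: 0.3 × 0.2 × 35.8 = 2.15 kPa; 2.15 / 12.5 = 17%.

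**Step 5. Effect on the test, on further assumptions.** Take 30 pairs, two-sided alpha 0.05, SD of differences 19.2 kPa (the SAP does not say whether its 19.2 is an SD of values or of differences), and s = 0.2 × 35.8 = 7.16 kPa. With no shift, the false-positive chance is 5% and power at 12.5 kPa is 93%.

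| Share changed (q) | Bias, kPa | % of 12.5 | False-positive chance | Power if the shift opposes the effect |
|---|---|---|---|---|
| 10% | 0.7 | 6% | 5.4% | 90% |
| 25% | 1.8 | 14% | 7.8% | 84% |
| 50% | 3.6 | 29% | 16.7% | 69% |

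With an SD of differences of 12 kPa, the false-positive chances become 6.2%, 12.4% and 35.2%, and power stays above 97%.

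**The case against.** The strongest reply is that the plan already restricts the comparator. It is not an arbitrary TE but the most recent on-treatment one within 3 months. The population is also described in terms that suggest response was judged on the current regimen: "Patients with CSPH considered responders to carvedilol prescribed twice daily were included". Among the record readings collected, the 3-month TE is the only on-treatment one from which the required SSM reduction of at least 10% could be derived. Part of this stands. The recency limit is real, and twice-daily dosing at the earlier TE is a fair inference. It remains an inference, because the responder rule names no TE, date or regimen. Even on the generous reading, it says nothing about an unchanged total daily dose.

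A reader might also infer several stronger points that the documents do not support:

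- **That the quality rule leaves out the record readings.** The IQR <30% rule is worded per patient and is not limited to the appointment. The fair criticism is that it is not expressly applied to the record value and has no handling rule. Random error in that value would mainly add variance.
- **That pairing the criterion as SSM or LSM biases the result.** Read literally, it could admit a patient with only an LSM in the window. That patient would contribute no SSM pair, which costs precision but does not shift the paired difference.
- **That the dose strata are misclassified.** The omitted dose is the current one, so grouping by current dose is defensible. The SAP does not say which date's dose is used, so misclassification is not shown.

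It is also fair to say that changes in both directions would partly cancel, and that every magnitude above rests on assumed inputs.

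**Conclusion.** The point holds in a limited form. Neither document requires the same total daily dose and twice-daily regimen at the comparator TE and at the appointment, and neither says that the dose at the comparator TE is recorded. Followed as written, the plan admits pairs whose difference mixes a dose or interval change with the omitted dose, and the planned analysis cannot separate them.

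The size is unknown. A bias of 0.4-2.1 kPa assumes that 10-30% of patients changed, with a 10-20% SSM shift all in one direction. A reader might infer that the result is biased, or that it is biased upward. The documents show neither: they do not report that any dose changed, and they give no direction. This is a cheap improvement to the plan, not evidence that the comparison fails.

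**What to change.** - **SAP, Data Collection:** add extraction of total daily carvedilol dose, dosing regimen and IQR/median at the comparator TE, from the same record as the stiffness values.
- **SAP, Data Analysis:** restrict the main comparison of appointment with previous TE, for SSM and likewise for LSM, to pairs with unchanged dose and regimen. Report the all-pairs result as a sensitivity analysis.
- **Quality rule:** state that the IQR <30% rule applies to the record value of the measure being analysed, so that an inadequate LSM does not remove a valid SSM pair.

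Handling this in data collection and analysis is preferable to rewriting the exclusion criterion. It still works if enrolment has closed, and it keeps affected patients visible in the sensitivity analysis.

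The cost is a few extra items from records already being opened, plus the loss of some pairs from the main analysis. How many cannot be told from the documents. With about 30 evaluable pairs expected, the number excluded should be reported.

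### Does the 24-hour marker for non-compliance conflict with the instruction on which carvedilol doses to omit before the scan?

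*SAP*

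**What the plan says.** The SAP (Participants) gives the instruction by dose: "Patients were asked to suspend the night dose of carvedilol and postpone the morning dose until LSM and SSM were measured". It goes on to say that "patients could be excluded from the study if they failed to comply to the study regimen", and explains this in brackets: "last dose of carvedilol within 24 hours or related with TE protocol, namely overnight fasting". Compliance is judged at the appointment.

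The Study Design section of the SAP names the resulting state by its length: "comparisons for under treatment with carvedilol and 24-hour suspension were stratified according to carvedilol daily dosage". The Protocol (Study design) uses the same 24-hour label, and both documents also describe the state as suspension of the second daily intake.

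The only carvedilol item listed for collection is the daily dose. The SAP (Data Collection) ends its list with "Child-Pugh score, and carvedilol daily dosage were collected", and the Protocol (Variables) ends with "Child-Pugh score, and carvedilol daily dosage". The Protocol's introduction says of carvedilol that "its half-life is approximately 7 to 10 hours".

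**The concern.** One condition is described in two ways, by doses omitted and by hours elapsed, and the two need not pick out the same patients. Someone who leaves out both doses took the last one the previous morning. If the scan is earlier in the day than that dose was, fewer than 24 hours have passed. That patient did what was asked and still meets the literal wording for exclusion.

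The exclusion is permissive and no tolerance is given, so such a case would be settled by judgement at the visit where stiffness is measured. Dosing interval is the subject of the study, and time since the last dose is close to being the exposure itself. If the times are not kept, a reader cannot check what interval the 24-hour label covers. At stake would be who enters the paired comparison and how the 10% allowance for not following the regimen is used up.

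**Working it through.** No figure in the plan is disputed here. The check asks when the two descriptions part, and how much that could matter.

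**1. When they part.** For a patient who follows the instruction,

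hours since last dose = 24 + (scan clock time − previous morning's dose clock time).

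The documents give no clock times, so those below are assumptions.

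| Last dose | Scan next day | Hours | Omitted both doses? | Last dose within 24 h? |
|---|---|---|---|---|
| 09:00 | 08:30 | 23.5 | yes | yes |
| 09:00 | 09:00 | 24.0 | yes | borderline |
| 09:00 | 09:30 | 24.5 | yes | no |
| 21:00 (night dose taken) | 08:30 | 11.5 | no | yes |

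Only the first row is a real conflict; the second depends on how an interval of exactly 24 hours is read. With morning doses anywhere from 07:00 to 10:00 and scans from 08:00 to 12:00, a patient who follows the instruction is between 24 + (8 − 10) = 22 and 24 + (12 − 7) = 29 hours from the last dose. This shows that a shortfall is possible, not that it happens.

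**2. What a shortfall means for exposure.** Inputs: the half-life of 7 to 10 hours from the Protocol's introduction, and simple exponential decay (my assumption). Drug remaining, as a percentage of the level at the last dose, is 100 × 0.5^(hours ÷ half-life).

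| Hours | Half-life 7 h | Half-life 10 h | Difference from 24 h (points) |
|---|---|---|---|
| 24.5 | 8.8 | 18.3 | −0.4 to −0.6 |
| 24 | 9.3 | 18.9 | 0 |
| 23.5 | 9.8 | 19.6 | +0.5 to +0.7 |
| 22 | 11.3 | 21.8 | +2.0 to +2.8 |
| 11.5 | 32.0 | 45.1 | +22.7 to +26.1 |

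Differences are taken before rounding. A half-hour shortfall is worth less than one point, and the lowest interval in the assumed clock range is worth two to three. The large contrast belongs to the patient who took the night dose, and that patient fails under both descriptions.

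**3. Bound on the result.** The SAP (Sample Size) plans for a rise of 48.3 − 35.8 = 12.5 kPa. The target of 33 less 10% leaves 33 × 0.9 = 29.7, about 30 patients. Suppose one borderline patient were kept and showed none of that rise. This is extreme, because the exposure is almost the same as at 24 hours. The mean change would fall by 12.5 ÷ 30 = 0.42 kPa, or 3.3% of the planned effect. If the patient were left out instead, one of about 30 pairs would be lost.

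**4. What the wording supports.** The 24-hour phrase is a bracketed explanation of failing the study regimen, and the only regimen described is the one in the sentence before it. A patient who left out both doses has followed that regimen. The instruction also speaks of postponing the morning dose, which makes sense only if the scan falls at or after the time it is due. With steady dosing times that gives 24 hours or more. A shortfall needs an unusually late dose the day before, or a scan ahead of the usual dose time.

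**5. The missing times.** The variable lists are not exhaustive. The Protocol's list omits spleen and liver stiffness, which are the outcomes, and body mass index, which is an exclusion criterion. The SAP does not list fasting as a data item, although it is checked. Applying a 24-hour marker at the appointment requires asking when the last dose was taken. The documents are silent only on whether the answer was written down.

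**The case for a change.** The strongest case for acting is that time since last dose is central to a study of dosing interval, that the exclusion is discretionary, and that it is exercised at the visit where the endpoint is measured, with no blinding of that decision described. A rule fixed in advance and two recorded times would remove the discretion at little cost.

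Part of this stands. The two descriptions can differ on a literal reading, no tolerance is given, and the times are not on either list. A report that gave hours since last dose, where known, and post-enrolment exclusions by reason would be easier to read.

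It does not reach the analysis. The discretion at issue covers only patients who left out both doses and fell slightly short of 24 hours. Those who took a dose they were asked to omit are non-compliant on either description, and the SAP's sample-size paragraph already counts failure to follow the regimen as a ground for exclusion. The SAP is also written in the past tense, so a tolerance set before the data are seen, or times newly recorded at the visit, may no longer be possible. Requiring an elapsed-time rule would in addition choose between wordings that are the sponsor's to reconcile.

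**Conclusion.** No change to the plan is needed. The mismatch is a gap in wording that the appointment check fills sensibly. It can arise only when the scan is earlier in the day than the previous morning's dose, and the documents give no sign that this occurs; the number of patients may be zero. Where it did occur, exposure would differ from that at 24 hours by under one percentage point for a half-hour shortfall and by two to three points at 22 hours. Even the extreme single-patient case shifts the mean change by about 0.4 kPa against a planned 12.5 kPa. The sample size and the paired tests stand as written.

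This rests on illustrative clock times, on one-exponential decay with the Protocol's half-life, and on reading the 24-hour phrase as an explanation of the regimen. The decay model says nothing about how stiffness responds to drug level. The instruction, the 24-hour label and the exclusion wording could be brought into line as an editorial matter. I take no position on which interval or marker is right.
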